15.0 Risks to Subjects

- If a parent chooses for their child not to participate, the risk is the same since regional anesthesia is part of standard care at MUSC and will be offered regardless of study participation. Both study medications have been routinely used in practice at MUSC for over ten years.
- Subjects will be assigned to receive intrathecal morphine or a quadratus lumborum block by chance. One group may prove to be less beneficial than the other.
- Intrathecal Duramorph/Morphine: the use is well established in pediatric patients even though it is not FDA approved for use in children, but is commonly used in this population and at this institution for this indication. Other risks include infection at site of injection (less than 1%), damage to surrounding structures (less than 1%), block failure (1%) headache and cerebral spinal fluid leak (7%), Urinary retention (6%), Nausea and vomiting are the most common risks/side effects occurring in less than 10% of patients. Itching occurs in 20-40% of patients. Literature states that patients recover from side effects and are not long term.

QL Block/Ropivacaine: complications/risks are rare but include local anesthetic systemic toxicity (less than 0.01%), block failure (1%), bleeding and infection at block site (less than 1%), damage to surrounding structures (less than 1%), allergic reaction (rare, less than 1%), neurological complications (less than 1%). Literature states that patients recover from side effects and are not long term.

- There is a risk of loss of confidentiality.

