4.0 Study Endpoints

- The primary endpoint will compare the effect that intrathecal morphine and quadratus lumborum blocks have on the duration of analgesia as demonstrated by charted pain scores and morphine equivalents in the first 24 hours.
- The secondary endpoint will assess the side effects of each intervention such as nausea and vomiting, and pruritis. Other secondary endpoints will include patient/family satisfaction, sedation, length of hospital stay, length of PACU stay, and analgesia for hospital stay (as approximated at 48 hours).

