- Approximately 24 hours after the procedure, a research team member will ask the parent/guardian about side effects such as nausea, vomiting, itching, etc. The research team member will also ask the family if they were satisfied with the subject's pain control postoperatively and overall experience. If a family member or guardian is not present, a care team member will be asked about side effects and the patient's chart will be reviewed for notes pertaining to side effects.
- The patient's chart will be used to see if and how much narcotic pain medication was administered in the first 48 hours after the procedure as well as documented pain scores up to 48 hours after the procedure ends. The chart medication administration record will also be used to identify administration of rescue medications for nausea

or itching non-opioid medications such as acetaminophen or ibuprofen, or other medications such as diazepam or oxybutynin.

Table 1. Baseline and Intraoperative Assessments	
Demographics	
Baseline	
Pre-op meds including opioids in past 24 hours	
Randomization	
Anesthesia intra-op data	
Surgical techniques	
Adverse Events	

Table 2. Post-Op Follow Up Assessments		
Outcome Measure	Instrument	Collected
Pain Scores	Charted pain scores	24 and 48 hrs. post-op
Pain Control Satisfaction	Parent/Guardian Satisfaction	24-hours post-op
Side Effects Experienced	Parent/Guardian Satisfaction	24-hours post-op
Overall Satisfaction	Parent/Guardian Satisfaction	24-hours post-op
Opioid Consumption	MME Consumption	24 and 48 hrs. post-op
Side Effects and Adverse Events	Adverse Events	Assessed through post-op hours 0-48
Medications	Medications used to control or relieve side effects	24 and 48 hrs. post-op

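### Headache/CSF leak (7%) and urinary retention (6%) after intrathecal morphine are not named as outcomes or in the interview wording, so they may be under-recorded

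*Combined protocol and SAP*

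**What the plan says.** The Objectives / Specific Aims section makes a higher side-effect incidence with ITM the second of two hypotheses.

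Section 15.0 puts a figure on seven ITM risks. Three are procedural (injection-site infection, damage to nearby structures, block failure), each at 1% or less. The other four are side effects in the patient:
- headache and CSF leak, and urinary retention: "headache and cerebral spinal fluid leak (7%), Urinary retention (6"%)
- nausea and vomiting: "Nausea and vomiting are the most common risks/side effects occurring in less than 10% of patients"
- itching: "Itching occurs in 20-40% of patients"

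The outcome wording names only the last two of these. Section 4.0: "The secondary endpoint will assess the side effects of each intervention such as nausea and vomiting, and pruritis". Section 12.0 repeats the same pair, limited to the first 48 hours. Sedation is a separate secondary outcome in both sections, and Section 12.0 adds oxygen saturation and supplemental oxygen in the PACU.

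In Section 10.0, a team member will, at about 24 hours, "ask the parent/guardian about side effects such as nausea, vomiting, itching, etc". If no family member is present, a care team member is asked and the chart notes are read. The narrative on rescue medication refers to nausea and itching. Table 2 has a wider row for drugs given against side effects, at 24 and 48 hours, and a general row for side effects and adverse events, "Assessed through post-op hours 0-48". Section 13.0 requires adverse events to be recorded and reported, without a time limit or an event list.

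Headache, CSF leak and urinary retention are mentioned nowhere outside Section 15.0.

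**The concern.** An event that is asked about by name is usually recorded more completely than one left to a general prompt. Here two ITM effects are named and two others, which the protocol itself puts at 6-7%, are not. Eligibility starts at 12 months (Section 5.0), and a child of that age cannot report a headache, so an observer has to be prompted to look for signs of one. Retention also needs one definition for both arms, because Section 5.0 gives ureteral reimplantation as the population of interest.

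What is at stake is the completeness of the side-effect description for a trial that hypothesises about side effects. If the unprompted events are partly missed, the reported ITM profile will look lighter than it was. An event after 48 hours, or after an earlier discharge, has no scheduled route into the dataset.

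**Working it through.** **Inputs.** ITM rates from Section 15.0: headache/CSF leak 0.07, urinary retention 0.06, nausea/vomiting below 0.10, itching 0.20 to 0.40. Group size from Section 12.0: 15 per arm, 30 in total (Section 6.0).

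**The plan's own figure.** Section 12.0 starts from 12 per group and inflates by 15% and then 10%: 12 × 1.15 × 1.10 = 15.18, stated as 15. This reproduces. It concerns morphine equivalents; no sample size is stated for side effects.

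**Expected ITM cases, n × p, with n = 15.**
- Headache/CSF leak: 15 × 0.07 = 1.05
- Urinary retention: 15 × 0.06 = 0.90
- Nausea/vomiting, at its ceiling: 15 × 0.10 = 1.50
- Itching: 15 × 0.20 = 3.0 to 15 × 0.40 = 6.0

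**Chance of at least one case, 1 − (1 − p)^n.**
- Headache/CSF leak: 1 − 0.93^15 = 0.663
- Urinary retention: 1 − 0.94^15 = 0.605 (0.6047, so 60%)
- Either event: 1 − (0.93 × 0.94)^15 = 0.867 if independent; 1 − 0.87^15 = 0.876 if they never occur in the same child

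If withdrawals leave 12 ITM children, the expected counts are 0.84 and 0.72, and the chances 58% and 52%.

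**Share of the quantified side effects.** The unnamed pair adds to 7 + 6 = 13 events per 100 ITM children. The named pair adds to 10 + 20 = 30 up to 10 + 40 = 50, with nausea/vomiting at its ceiling. The unnamed share is 13/63 = 21% to 13/43 = 30%.

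**Effect of incomplete capture.** The documents give no capture rate, so this is an assumption with a range. Expected recorded cases of the two events together are 15 × 0.13 × c:
- c = 1: 1.95
- c = 0.75: 1.46
- c = 0.5: 0.98
- c = 0.25: 0.49

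At c = 0.5 the chance of recording at least one case falls to 1 − 0.965^15 = 41% for headache/CSF leak and 1 − 0.97^15 = 37% for retention.

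**Could naming the events support a test between arms?** No. With no QL case, 4 of 15 ITM cases give a two-sided Fisher p of 2 × 1365/27405 = 0.0996, and 5 of 15 give 2 × 3003/142506 = 0.042. Five cases would be needed where about one is expected. Taking the QL rate as 0 to 1% (an assumption), exact power is 0.24-0.28% for headache/CSF leak and 0.12-0.14% for retention. Against an assumed 1% in QL, 80% power would need about 167 and 211 per arm.

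**The case against.** The strongest reply is that the plan does not exclude these events. The outcome and interview lists are given as examples, so they are open, and the interview form itself is not in the documents. Table 2 covers all side effects and adverse events to 48 hours in both arms and has a row for any drug given against a side effect. Section 13.0 requires adverse-event recording with no 48-hour cut-off. Sedation and PACU oxygen measures are further harm outcomes. All of this stands. It limits the point to events that are not solicited by name. It does not remove the point: the general adverse-event row has no list, definition or prompt, and reading chart notes for side effects is described only for when the family is absent.

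A reader might infer more than the documents support:
- *That these events distinguish the arms.* Section 15.0 lists them for ITM only, but its QL list also omits nausea, vomiting and itching. Absence from that list is not a zero rate, and no QL rate is given.
- *That a known share falls after 48 hours.* No onset times are given, so no share can be stated.
- *That a test is biased.* No composite side-effect score and no specific side-effect test is set out, and about one case of each event could not drive one.
- *That the unnamed events are as frequent as all the named ones.* They are close to nausea/vomiting, but itching is put at roughly 3 to 7 times either figure (20/7 to 40/6).

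**Conclusion.** The point holds as one of ascertainment. Two ITM side effects that the protocol puts at 7% and 6% are not prespecified or solicited by name, and scheduled assessment of them ends at 48 hours. They may be under-recorded relative to the solicited effects, which can understate ITM side effects descriptively. Whether the difference between arms would also shift depends on QL rates that the documents do not give.

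The size is about one expected case of each event in 15 ITM children. The chance that at least one of the two occurs is about 87-88%, so the trial will probably meet such a case and how it is captured matters. This rests on Section 15.0's rates applying to this population and on 15 treated ITM children; the actual loss in capture is unknown. The primary analysis and sample size are unaffected. The change should be made, but its gain is complete description and safety capture, not statistical power.

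**What to change.** - In Sections 4.0, 10.0 and 12.0 and in Table 2, name headache/CSF leak and urinary retention as descriptive side-effect outcomes, collected identically in both arms. Take retention from charted events under one written definition.
- At the 24-hour interview, ask about both explicitly, with an observer-based prompt for preverbal children. Use the same questions when a care team member answers.
- Extend the chart check for these two events, injection-site infection and neurological symptoms from 48 hours to discharge and, where available, the first routine postoperative record. Length of hospital stay is already an outcome, so the stay already has to be followed to discharge.
- Report counts and proportions by arm, without a formal test.

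The cost is two more interview questions and one later chart check in 30 children. The drawback is that late events will still depend on routine charting, so a zero after 48 hours should be reported as none charted, not none occurred.

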16.0 Potential Benefits to Subjects or Others

- There are no direct benefits to subjects or their families for participation in this study.
- There is a potential benefit that the subject's participation in the study may contribute to knowledge of this area of practice and may impact patient care in the future.

17.0 Sharing of Results with Subjects

- Results will not be shared with participants or their families.

18.0 Drugs or Devices

- The intrathecal morphine will be prepared in the pharmacy by a licensed pharmacist under a sterile hood; the local anesthetic for quadratus lumborum block will be drawn immediately preceding the block from a sterile vial in a sterile operating room by a board-certified pediatric anesthesia attending participating in the study.
- The contents of the injectate will be based off the patient's randomly assigned group.
- The pharmacist will not be blinded to the randomization. Nor will the operative team. The study team member who completes data collection from the family and chart review will be blinded to randomization, as well as the child and parent.
- The drugs used in this study, morphine and ropivacaine, are FDA approved for use in this manner for adults; they have not been FDA approved for children, although they are used regularly as part of standard of care. Intrathecal morphine has been shown to

be safe in pediatric patients for major surgeries. In a recent retrospective study by Keskin et al [6], of 100 children who received 5 mcg/kg intrathecal morphine for major surgery for postoperative analgesia there were no serious adverse events (minor side effects of pruritis and nausea/vomiting seen in small number of patients, 14 and 9 patients respectively). An additional retrospective review from CHOP of 187 pediatric patients concluded that ITM in this population is a useful and safe analgesic adjunct [4]. The usage of intrathecal morphine in pediatric patients undergoing major spinal surgery is well established and without report of major adverse events [7,8]. Ropivacaine use is well established in pediatric patients, whether administered neurally (epidural or caudal) or for peripheral nerve block. The European Society of Regional Anesthesia and American Society of Regional Anesthesia published a joint recommendation on local anesthetic use for regional/neuraxial anesthesia in pediatric patients which included dosing strategies for ropivacaine [10].

References

